**PROMOTOR**

**INSTITUT BERGONIÉ**

## SUMMARY

PROMOTOR	Institut Bergonié
PRINCIPAL INVESTIGATOR / COORDINATOR	[name] [name]
RESEARCH LEAD	[name] [name]
ACRONYM	TS-PAC
TITLE	Remote monitoring for ambulatory care of elderly patients with cancer. The TS-PAC study
RATIONALE / CONTEXT	
In France, more than half of patients with cancer are over 65 years old. The majority of these elderly patients have geriatric fragilities (Caillet et al., 2014; Mohile et al., 2011), exposing them to increased risks of toxicity from cancer treatments (Extermann et al., 2012; Ruiz et al., 2019), but also to undesirable reactions to complications or unscheduled hospitalizations. Elderly patients also have different expectations to younger patients regarding the goals and consequences of cancer treatments, emphasizing the maintenance of quality of life and independence, at the expense of quantity of life (Fried et al. al., 2002).
 
To provide better care for these patients, it is therefore important to diagnose toxicities and treatment complications as early as possible and to respond to these better, anticipating possible hospitalizations. Further, there is a need to identify tumor events (progression, relapses) early and to treat patients before their general condition deteriorates. We must fully appreciate the benefits of treatments for patients, not only on tumor control but also on quality of life and autonomy.
 
Telemedicine and connected health tools seem to be able to improve the care of these patients. In the STAR (Basch et al., 2016, 2017) and SENTINEL (Denis et al., 2017) studies patients undergoing chemotherapy or having completed their treatment received weekly remote monitoring via an online questionnaire concerning 12 symptoms. This helped improve quality of life, reduce emergency department visits and unscheduled hospitalizations, detect tumor progression earlier, start treatment in patients in better general condition, and thus lengthened overall survival.
 
In addition, patient-reported outcomes (PRO) have been shown to be useful to tailor medical management and assess prognosis. PRO collection enables better detection of symptoms by the doctor (Detmar et al., 2002; Montemurro et al., 2016) and a more accurate estimate of their severity (Novello et al., 2014), especially for subjective symptoms (Basch et al., 2006). This leads to therapeutic adaptations, reduces subsequent

	
undesirable effects and improves quality of life. In addition, a patient's subjective assessment of his/her quality of life and state of health at the start of treatment (for example with the QLQ-C30 questionnaire) is correlated with overall survival (Gotay et al., 2008; Lee et al., 2018; Maione et al., 2005; Quinten et al., 2009; Sloan et al., 2012). Improvement in or deterioration of quality of life during treatment is also correlated with survival (Eton et al., 2003; Vickers et al., 2016), probably due to the direct effect of treatment on cancer symptoms. However, this is also likely to be due to the supportive care that improves both quality of life and overall survival (Temel et al., 2010), irrespective of treatment efficacy.
 
The TS-PAC study therefore aims to develop a remote monitoring tool enabling the weekly collection of symptoms reported by elderly patients during cancer treatment, to detect early any toxicities and unfavorable changes which might require specific management. This tool will also make it possible to collect patient self-reports of perceived benefits observed following treatment in addition to the clinical parameters usually assessed (e.g. tumor control, progression-free survival and overall survival).


OBJECTIVES
	
Primary objective
 
To assess the feasibility of using an online remote monitoring tool during the care of patients over the age of 65 who are receiving medical treatment for cancer.
 
Secondary objectives
 
 
• To evaluate and describe the responses to the self-questionnaires available on the remote monitoring tool: 
 
o Number of toxicities and clinical symptoms reported by patients triggering a “red” alert.
 
o Compliance (for patients on oral therapy).
 
o Subjective evaluation of the benefit provided by the treatment.
 
o Satisfaction with the use of the remote monitoring tool.
 
o Quality of life relative to patient health (EORTC QLQ-C30 and QLQ-ELD14).
 
o Depression and anxiety in patients (HAD scale).
 
 
 
• To evaluate and describe the other parameters collected by the coordinating nurse during telephone and / or clinical follow-up: 
 
o Risk of drug-related iatrogenesis.
 
o Autonomy for activities of daily living using the ADL and IADL scales.
 
o Geriatric frailty of patients using the G8 score and, if necessary, an onco-geriatric assessment.
 
o Precariousness of patients with the EPICES score.
 
o Distance and travel time to the care facility.
 
o Computer experience.
 
o Number of unscheduled hospitalizations and reasons.
 
 
 
• To describe the feasibility of using the tool at the different evaluation points according to patient characteristics at inclusion: 
 
o Risk of drug-related iatrogenesis.
 
o Autonomy for activities of daily living.
 
o Geriatric fragility of patients.
 
o Precariousness of patients with the EPICES score.
 
o Distance and travel time to the care facility.
 
o Computer experience.
 
 
 

	
 
• To evaluate technical procedures for the remote monitoring tool.
 
• Describe the remote monitoring process (number or rate of alerts by level of severity, patient management following alerts triggered by the tool, number of telephone reminders made by the Coordinating Nurse to the patient).
 

ENDPOINTS	
Primary endpoint:
 
The primary endpoint is the proportion of patients who completed at least all of the following questionnaires at 3 months (9 questionnaires in total):
 
 
• Six weekly questionnaires on toxicities and clinical symptoms completed within 3 months of the start of treatment: 
 
o Toxicities and clinical symptoms will be assessed through 20 questions selected and adapted from the French version of the PRO (patient-reported outcomes) of the CTCAE (Common Terminology Criteria for Adverse Events) (Basch et al., 2014; National Cancer Institute, 2017).
 
o A weekly questionnaire on toxicities and clinical symptoms will be considered complete if the patient has answered the first 7 mandatory questions (out of the 20 items).
 
 
 
• Two questionnaires assessing the health-related quality of life, completed before the start of treatment and at 3 months: 
 
o Quality of life (QOL) will be assessed using the EORTC QLQ-C30 questionnaire (Aaronson et al., JNCI 1993) comprising 30 items. The targeted dimensions of the QLQ-C30 will be the five functional scales (physical, daily activity, emotional, cognitive and social) and the overall quality of life scale.
 
o A QOL questionnaire will be considered complete if the scores of the 5 functional scales and the overall QOL score are calculable (more than 50% of the items of each sub-scale answered) according to the EORTC scoring manual.
 
 
 
• The questionnaire evaluating the perceived benefit of the treatment at 3 months. The questionnaire will be considered as complete if the patient has answered the first question: "How effective do you find your cancer treatment?"
 
 
Secondary endpoints:
 
Answers to the self-questionnaires available on the remote monitoring tool
 
 
• Toxicities and symptoms will be assessed weekly using 20 questions selected and adapted from the French version of the CTCAE PRO (Basch et al., 2014; National Cancer Institute, 2017). For each question, predetermined response thresholds have been established, triggering "orange" (to watch) or "red" alerts (intervention by the healthcare team required). The number of red alerts will be collected for each patient.
 
• The subjective evaluation of the perceived benefit of treatment will be evaluated at 3 and 6 months by a questionnaire developed specifically for this project.
 
• Patient satisfaction with the use of the remote monitoring tool will be evaluated at 3 and 6 months by a questionnaire developed specifically for this project.
 
• Quality of life will be assessed at inclusion, 3 months and 6 months using the EORTC QLQ-C30 questionnaire (Aaronson et al., JNCI 1993) and, for people over 70 years old, using the QLQ-ELD14 module specifically for the elderly (Wheelwright et al., 2013). The targeted dimensions of the QLQ-C30
 


	
will be the 5 functional scales (physical, daily life, emotional, cognitive, and social) and the overall quality of life scale.
 
 
• Depression and anxiety will be assessed at baseline, 3 months and 6 months, using the HAD questionnaire (Zigmond and Snaith, 1983).
 
 
Parameters collected by the Coordinating Nurse during telephone and / or clinical follow-up
 
At inclusion:
 
 
• The risk of drug-related iatrogenesis will be assessed by collecting the number of different drugs taken by the patient (Queneau et al., 2007).
 
• Patient autonomy for activities of daily living will be assessed using two scales: the ADL scale (Katz et al., 1963) and the IADL scale (Lawton and Brody, 1969).
 
• The geriatric frailty of patients will be assessed using the G8 score for patients aged 70 and over (Soubeyran et al., 2014), and if necessary, using a standardized geriatric assessment (EGS). Geriatric interventions will be described by domain. Patients will be separated and described according to 3 groups reflecting their frailty: (1) patients under 70 years old and over 70 years old with a G8 score > 14, (2) patients over 70 years old with a G8 score ≤ 14 having had an EGS without intervention, and (3) patients over 70 years of age with a G8 score ≤ 14 having had an EGS with geriatric intervention.
 
• Patient precariousness will be assessed using the EPICES (Evaluation of Deprivation and Inequalities in Health Examination Centres) score (Labbé et al., 2007).
 
• The distance between the place of residence and facility where the care is delivered, as well as the average time required for this journey, will be evaluated (collection of the place of residence).
 
• Patients' computer experience will be evaluated (regular access to a computer, tablet or smartphone, to send emails and / or use applications and / or search the Internet).
 
 
At 3 months and 6 months:
 
 
• The number of unscheduled hospitalizations > 24 hours and the number of emergency room visits, as well as their reason, will be assessed.
 
 
Feasibility of using the tool at different evaluation times depending on the characteristics of the patients at inclusion
 
The feasibility of using the tool is defined as for the primary endpoint. The completion rates of the online questionnaires will be described at 3 months and 6 months according to the following parameters at inclusion:
 
 
• Risk of drug-related iatrogenesis.
 
• Autonomy for activities of daily living.
 
• Geriatric frailty of patients.
 
• EPICES precariousness score.
 
• Distance and travel time to the care facility.
 
• Computer experience.
 
 
Technical details when using the remote monitoring tool.
 
The technical procedures when using the remote monitoring tool will be assessed by collecting the following parameters:
 
 
• Type of device on which the application is used (e.g. smartphone, tablet, or computer).
 
• Number of times the software bugs or crashes
 
• Management of the failure by Coordinating Nurse or by the supplier.
 

--	--

	
Description of the monitoring process
 
The remote monitoring process will be described by:
 
 
• The number and / or rate of alerts generated by the tool depending on the severity level of the alert.
 
• The nature and number of actions implemented and interventions carried out.
 

RESEARCH DESIGN	Single-center, prospective cohort pilot study evaluating the feasibility of a online remote monitoring tool during the care of patients over 65 years of age being medically treated for cancer.
INCLUSION CRITERIA	
 
1. Patients 65 years of age and over.
 
2. Histologically proven cancer: breast, lung, ovary, prostate, bladder, kidney, ENT, colon-rectum, melanoma, sarcoma, lymphoma, myeloma, or myelodysplastic syndrome.
 
3. Included before starting medical treatment (chemotherapy, hormone therapy, targeted therapy, immunotherapy or combination).
 
4. Informed consent dated and signed.
 
5. Patients affiliated with a French social security scheme in accordance with the French law on biomedical research (Article 1121-11 of the French Code of Public Health).
 

NON INCLUSION CRITERIA	
 
1. Life expectancy less than 12 months.
 
2. Patient declining to use a tablet, computer, smartphone or the Internet.
 
3. Patient not knowing how to read and understand French.
 
4. Technical impossibility of connecting to the Internet in the patient's living area.
 
5. Patient already included in this study or in another study evaluating a remote monitoring system.
 


STUDY PROCEDURE
	
Each patient will have to answer the remote monitoring questionnaires on a mobile phone, tablet or computer via the Internet. Responses will be sent to the referring oncologist and team (Coordinating Nurse). For each question, predetermined response thresholds have been established, triggering "orange" (to watch) or "red" alerts (intervention by the healthcare team required).
 
Follow-up by self-questionnaire is as follows:
 
 
• Weekly: toxicity and clinical symptom assessment questionnaire.
 
• Every 3 months: QLQ-C30 +/- ELD14 quality of life questionnaires, HAD anxiety and depression assessment questionnaire, questionnaire for the subjective assessment of perceived benefit of treatment, and client satisfaction with use of the tool questionnaire.
 
 
If a "red" alert is triggered, the team will decide on the type of intervention which can be:
 
 
• A phone call to the patient
 
• A change in treatment
 
• Prescription of supportive oncological care
 
• A consultation.
 
• Hospitalization.
 
• The intervention of a local health professional (attending physician, nurse).
 
• The transmission of potentially useful information to the patient's pharmacist.
 
 
Alerts will be raised by the Coordinating Nurse within 24 hours during the week, Monday to Friday, 9 a.m. to 5 p.m. excluding public holidays. The Nurse will be available and contactable directly if necessary during these hours. This is not 24 hour surveillance. Patients will be warned that in an emergency, they should systematically contact their attending physician or the ambulance (SAMU) outside of these time slots.
 
In parallel, patient will continue standard follow-up with their referring oncologist and, if necessary (age <math>\geq 70</math> years and G8 score <math>\leq 14</math>), will benefit from an onco-geriatric evaluation at inclusion then at 3 and 6 months.
 
At the end of 6 months of remote monitoring, the Coordinating Nurse will inform the patient of the end of study participation. Within one month of the end of the remote monitoring, the nurse will also proceed to the remote uninstallation of the application and will organize the return of the equipment (tablet and/or 3/4G key) if these were lent for the study.


SIZE OF STUDY
	
The primary endpoint is the proportion of patients who completed at least 9 questionnaires at 3 months: 6 weekly toxicities / clinical symptoms questionnaires (20 items including 7 mandatory) + 2 EORTC QLQ-C30 quality of life questionnaires (30 items, mandatory scores for the 5 functional scales + the overall QOL) + 1 questionnaire evaluating the benefit of the treatment perceived by the patient (3 items, 1st question mandatory).
 
Based on the results of other feasibility studies on remote monitoring in oncology (SENTINEL (Denis et al., 2014), STAR (Judson et al., 2013) and e-DomSanté1 (Quénel-Tueux et al., 2018)), we will consider the use of our online tool for the remote monitoring of elderly patients with cancer as feasible if 75% of the patients included and having started medical

	
treatment against cancer answer all the questionnaires defined in the primary endpoint criterion. The inclusion of 30 eligible and evaluable patients will allow us to estimate this rate of 75% of patients who answered all the questionnaires (9 in total) with a 95% confidence interval on a bilateral basis of (55.6% - 88.2%). The confidence interval was calculated using Wilson's method with continuity correction. Estimating that 10% of patients will not be eligible / evaluable, we estimate that 33 patients should be included.

RESEARCH DURATION	
Duration of the inclusion period: 24 months  Duration of participation of each participant: 6 months  Total duration of research: 30 months

STATISTICAL ANALYSIS	
Analysis populations
 
 
• Eligible population: all patients included with no major deviations from the eligibility criteria.
 
• Eligible and assessable population: eligible patients who started medical treatment (chemotherapy, hormone therapy, targeted therapy, immunotherapy or combination).
 
 
Statistical analyses:
 
 
• The primary endpoint will be calculated from the eligible and assessable population.
 
• The proportion of patients who completed 9 questionnaires at three months will be calculated as follows: number of eligible and assessable patients who completed the 9 questionnaires at 3 months divided by the number of eligible and assessable patients. The proportion will be reported with its 95% confidence interval (binomial law).
 
• The secondary endpoints will be calculated from the eligible and assessable population as for the primary endpoint.
 
• The scores of the questionnaires (continuous variables) will be described on the basis of means (+/- standard deviation) if the normality hypothesis is satisfied, and failing that, on the basis of other descriptive statistics (median, range, quartiles).
 
• The scores can be categorized according to the thresholds described in the literature. For each questionnaire, the proportion of patients with a score above or below the predefined threshold will then be reported with its 95% confidence interval (binomial law).
 
• The quantitative variables will be described from the mean and the standard deviation if the assumption of normality is respected, failing other descriptive statistics will be used (minimum, maximum, median and quartiles).
 
• The qualitative variables will be described on the basis of the numbers and associated frequencies, expressed as a percentage (%).
 
 
For each variable, the number of missing data will be described. Whenever possible, the reasons will be documented to assist the interpretation of results.


EXPECTED OUTCOMES
	
To assess the feasibility of using an online tool for elderly patients.
 
Improve the coordination of care between hospital and home health professionals.
 
Create a new strategy for monitoring patients undergoing treatment for cancer, to optimize their care pathway, and to reduce health inequalities that may affect elderly patients at risk due to their geriatric fragility.
 
Introduce patient-reported outcomes into standard care which will thus be more centered around the patient, empowering the patient. PRO collected from elderly patients can also be used routinely, to educate caregivers to take into account the most frequent symptoms, but also in future therapeutic trials on elderly cancer patients.

---------------------------------	---

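### Frailty group 1 pools unscreened patients aged 65-69 with older patients who screened non-frail, so the description of completion by frailty mixes age and missing screening with frailty

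*Combined protocol and SAP*

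**What the plan says.** All references are to the Summary of the combined protocol and SAP.

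- **INCLUSION CRITERIA**, item 1: "Patients 65 years of age and over".
- **ENDPOINTS**, nurse-collected parameters at inclusion: "The geriatric frailty of patients will be assessed using the G8 score for patients aged 70 and over", followed if necessary by a standardized geriatric assessment (EGS).
- **Same bullet**: "Patients will be separated and described according to 3 groups reflecting their frailty". Group 1 is "1) patients under 70 years old and over 70 years old with a G8 score" above 14. Groups 2 and 3 are patients over 70 with a G8 of 14 or less, the former "having had an EGS without intervention" and the latter "having had an EGS with geriatric intervention".
- **STUDY PROCEDURE**: patients aged 70 or more with a G8 of 14 or less "will benefit from an onco-geriatric evaluation at inclusion then at 3 and 6 months".
- **ENDPOINTS**, feasibility by patient characteristics: "The completion rates of the online questionnaires will be described at 3 months and 6 months according to the following parameters at inclusion". Geriatric frailty is one of the six parameters listed, and the matching secondary objective stands under OBJECTIVES.

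**The concern.** A patient aged 65-69 has no G8 result, so on this scale the frailty status is unknown. Group 1 nevertheless places that patient with people aged 70 and over whose G8 was above 14. Not screened is thus reported as if it meant screened and non-frail. The plan's own RATIONALE / CONTEXT gives no support for presuming this: it says that most cancer patients over 65 have geriatric fragilities. That statement covers the over-65s as a whole and does not single out ages 65-69, but it is the only indication the document gives.

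Age is also tied to the grouping. All patients under 70 are in group 1 and none are in groups 2 or 3. If completion is higher in group 1, the reader cannot tell whether the cause is less frailty or younger age. If frail patients aged 65-69 complete less often, their presence lowers the group 1 rate and narrows the visible gap. At stake is the one table that would show whether frail older patients can use the tool.

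**Working it through.** **Step 1. Reproduce the plan's figure.** SIZE OF STUDY gives 30 evaluable patients, an expected rate of 75% and a 95% interval of 55.6%-88.2% by Wilson's method with continuity correction. With p = 0.75, q = 0.25, n = 30, z = 1.96:

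- lower = [2np + z² − 1 − z√(z² − 2 − 1/n + 4p(nq + 1))] / [2(n + z²)] = 55.55%
- upper = [2np + z² + 1 + z√(z² + 2 − 1/n + 4p(nq − 1))] / [2(n + z²)] = 88.21%

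The figure reproduces. The present point does not depend on it, but it fixes n = 30 and the interval method used below.

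**Step 2. Place each kind of patient in the groups, taking the wording literally.**

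| Age | G8 | EGS | Group |
|---|---|---|---|
| 65-69 | not given | not triggered | 1 |
| exactly 70 | any | any | none |
| over 70 | > 14 | not triggered | 1 |
| over 70 | ≤ 14 | done, no intervention | 2 |
| over 70 | ≤ 14 | done, intervention | 3 |
| over 70 | ≤ 14 | not done | none |
| over 70 | missing | any | none |

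The first and third rows share group 1. That is a stated rule, not an omission. The three rows without a group are weaker points and are taken up under the objection.

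**Step 3. How large could the mixing be?** The documents give no age or G8 distribution, so the inputs are assumptions:

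- f = share of the 30 aged 65-69: 10% to 50%
- s = share of those aged 70 and over with G8 ≤ 14: 50% to 70%
- r = share of those aged 65-69 who would have scored ≤ 14 if tested: 20% to 60%

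Formulas: unscreened patients U = 30f; size of group 1 G = 30f + 30(1 − f)(1 − s); potentially misclassified M = 30fr.

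| f | s | U | G | U/G | M (r = 20% to 60%) | M/G |
|---|---|---|---|---|---|---|
| 10% | 50% | 3 | 16.5 | 18% | 0.6 to 1.8 | 4% to 11% |
| 10% | 70% | 3 | 11.1 | 27% | 0.6 to 1.8 | 5% to 16% |
| 30% | 50% | 9 | 19.5 | 46% | 1.8 to 5.4 | 9% to 28% |
| 30% | 70% | 9 | 15.3 | 59% | 1.8 to 5.4 | 12% to 35% |
| 50% | 50% | 15 | 22.5 | 67% | 3 to 9 | 13% to 40% |
| 50% | 70% | 15 | 19.5 | 77% | 3 to 9 | 15% to 46% |

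**Step 4. Effect on the reported rate.** Suppose, for illustration only, that completion were 85% with G8 > 14 and 60% with G8 ≤ 14, at any age. Group 1 would then show 0.85 − 0.25 × M/G: from 0.85 − 0.25 × 0.036 = 84% to 0.85 − 0.25 × 0.462 = 73%, against 85% in patients who truly score above 14. If r were zero, nobody would be misclassified and the rate would stay at 85%; the mixing of age with frailty would remain.

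**The case against.** The strongest reply is that the table is only descriptive. OBJECTIVES and ENDPOINTS say that completion will be described by inclusion characteristics, STATISTICAL ANALYSIS lists no between-group test, and frailty is one of six factors in a pilot of about 30 patients. The groups also follow the study's own pathway: no assessment triggered, assessed without intervention, assessed with intervention. ADL, IADL and the number of drugs have no age limit, so patients aged 65-69 are partly characterized elsewhere. All of this stands and limits the weight of the point. It does not remove it: the plan calls the groups a reflection of frailty, and the other measures are separate parameters that do not repair this grouping.

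Three stronger readings are tempting, and the documents do not support them.

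- *Patients will be misclassified.* This needs some patients aged 65-69 to be frail by the G8. The rationale makes it plausible, but nothing in the documents shows how many there would be.
- *Patients aged exactly 70 fall out of the analysis.* The same bullet applies the G8 from 70, and STUDY PROCEDURE uses the same threshold. The document also writes over 65 where the inclusion criterion is 65 and over. In context, over 70 is loose wording for 70 and over.
- *Frail patients without an EGS drop out unseen and are the least compliant.* STUDY PROCEDURE plans an evaluation at inclusion for every patient aged 70 or more with a G8 of 14 or less, so the gap arises only if a planned assessment is missed. STATISTICAL ANALYSIS would then report it as missing data, with reasons where possible. It gives no rule for placing such a patient in a group, but nothing in the documents speaks to that patient's compliance.

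**Conclusion.** The point holds in limited form. Group 1 equates not screened with screened non-frail and mixes age with frailty in the secondary description of completion by frailty. This follows from the text alone and needs no assumption beyond the enrolment of some patients aged 65-69, which the inclusion criteria allow.

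The size cannot be derived from the documents. Under the assumed ranges, 18% to 77% of group 1 would be unscreened, and 0.6 to 9 patients (4% to 46% of the group) would be counted as non-frail although they would have scored 14 or less. The drop in the reported rate from 85% to between 84% and 73% rests further on the illustrative completion rates. The primary endpoint, its denominator and the sample size are unaffected. This is a cheap improvement to a secondary descriptive table.

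**What to change.** In the ENDPOINTS definition of the frailty groups, and in the table of completion by frailty at 3 and 6 months:

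1. Show patients aged 65-69 as their own stratum, labelled not screened (under 70).
2. Write 70 and over in all the other groups, to match the G8 rule and STUDY PROCEDURE.
3. Keep three separate groups from age 70: G8 > 14; G8 ≤ 14 with EGS and no intervention; G8 ≤ 14 with EGS and intervention.
4. Put any patient aged 70 or more with a missing G8, or with G8 ≤ 14 and no EGS done, in a separate category. Do not merge these patients with assessed ones, which would repeat the fault.
5. Describe completion for G8 ≤ 14 and for G8 > 14 among patients aged 70 and over, each with its confidence interval and without a test.

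The change needs only wording and uses age, G8 and EGS status already collected. The cost is smaller cells. By the plan's own interval method, 9 of 12 completing gives 42.8%-93.3% and 4 of 5 gives 29.9%-99.0%, against 55.6%-88.2% for the whole sample at 75%. Strata of this size say little on their own, and the report should say so.

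### The summary lists no item on who entered the online answers, so forms entered at home by a relative would go undetected and count toward the 75% feasibility criterion

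*Combined protocol and SAP*

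**What the plan says.** **Intended respondent.** The Study procedure section of the summary states: "Each patient will have to answer the remote monitoring questionnaires on a mobile phone, tablet or computer via the Internet". It calls the follow-up forms self-questionnaires.

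**Primary endpoint.** Under Endpoints: "The primary endpoint is the proportion of patients who completed at least all of the following questionnaires at 3 months". Nine forms are required: six weekly symptom forms, two QLQ-C30 forms and one perceived-benefit form. The weekly and perceived-benefit forms are complete when the patient has answered the mandatory question or questions. The QLQ-C30 rule asks only that the functional and overall scores can be calculated.

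**What is recorded about use of the tool.** The technical parameters begin with "Type of device on which the application is used (e.g. smartphone, tablet, or computer" and continue with software failures and who dealt with them. The process data are alerts and the actions taken, plus telephone reminders in the Objectives. Autonomy (ADL, IADL), frailty and computer experience are collected at inclusion. They describe the patient, not the person who enters a given form.

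**Decision rule and analysis.** Under Size of study, the tool is regarded "as feasible if 75% of the patients included and having started medical" treatment complete all the required forms. The Statistical analysis section divides completers by eligible and assessable patients. It has no respondent check and no sensitivity analysis on this point.

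**The concern.** The forms are answered remotely, by patients aged 65 and over. Declining to use a device or the Internet is a reason for non-inclusion; being unable to use one unaided is not. The plan itself expects computer experience and autonomy to vary enough to be worth describing. A spouse or child could therefore enter the answers at home, and nothing listed in the summary would show it.

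Three results are exposed:

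- **The completion rate.** It could reflect an available helper rather than use of the tool by the patient, and the report could not tell the two apart.
- **Completion by patient characteristics.** If the least able patients receive the most help, differences by autonomy, frailty or computer experience would shrink. This is a possibility; the documents neither show it nor rule it out.
- **The answers themselves.** Symptom, QLQ-C30, HAD and perceived-benefit results would mix patient and proxy reports under the label of patient-reported outcomes.

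Who entered a form cannot be reliably reconstructed afterwards, so the information has to be collected prospectively.

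**Working it through.** **Inputs from the summary (Size of study, Endpoints, Study procedure)**

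- Feasibility criterion: 75%.
- Evaluable patients: 30.
- Stated two-sided 95% interval for a rate of 75%: 55.6% to 88.2%, by Wilson's method with continuity correction.
- Six weekly forms needed within 3 months, on a weekly schedule.

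**Assumed inputs (not in the documents)**

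- Apparent completion rate: 80%.
- Share *f* of completers whose status depends on a relative answering for them: 5%, 10% or 20%.

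**1. Reproduce the plan's interval.** With p = 0.75, q = 0.25, n = 30, z = 1.96:

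- Lower = [2np + z² − 1 − z√(z² − 2 − 1/n + 4p(nq + 1))] / [2(n + z²)] = (47.84 − 10.24)/67.68 = 55.6%
- Upper = [2np + z² + 1 + z√(z² + 2 − 1/n + 4p(nq − 1))] / [2(n + z²)] = (49.84 + 9.86)/67.68 = 88.2%

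Both limits match the plan.

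**2. Pass mark.** 0.75 × 30 = 22.5, so 23 completers are needed. 23/30 = 76.7% passes and 22/30 = 73.3% does not. Each patient is worth 1/30 = 3.3 percentage points.

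**3. Effect of undetected proxy entry.** Patient-entered rate = 0.80 × (1 − f). Chance of passing = P(X ≥ 23), X binomial with n = 30 and that rate.

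| Share of completers depending on a relative (assumed) | Patient-entered rate | Chance of reaching 23/30 |
|---|---|---|
| 0% | 80% | 0.76 |
| 5% | 0.80 × 0.95 = 76% | 0.57 |
| 10% | 0.80 × 0.90 = 72% | 0.37 |
| 20% | 0.80 × 0.80 = 64% | 0.10 |

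The first row is the chance of passing that the study would show in every case, because proxy entry is not seen. The other rows are the chance if only patient-entered forms counted.

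**4. Slack in the endpoint.** Three months of weekly forms give about 12 opportunities, and six are needed, so about six are spare. An occasional weekly form entered by a relative need not change a patient's status. There is no such slack for the two QLQ-C30 forms or the perceived-benefit form: each is required, at a fixed time. The share *f* above refers to patients who would not be completers without the proxy-entered forms, not to every patient with one such form.

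**The case against.** **The plan does not accept proxy forms.** A reader might infer that the rules count a relative's answers as the patient's. They do not. The forms are self-questionnaires, and for the weekly and perceived-benefit forms it is the patient who must answer. Entry by a relative would depart from those rules. What stands is that the departure could not be seen.

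**Not every item is visible.** A reader might infer that nothing in the study records who responded. The documents do not support that. The satisfaction questionnaire was developed for this project and its items are not shown; it could include a question on help received. Even so, it is given at 3 and 6 months only and would not label each weekly form.

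**Assisted use may be legitimate.** The primary objective concerns use of the tool in the care of older patients and does not say unaided. Completion with family help can be part of real-world feasibility. This stands. It is a reason to distinguish help from proxy entry and to leave the primary rule alone, and it does not remove the value of knowing which occurred.

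**The arithmetic could be read too strongly.** At 23/30 one patient reverses the result, whatever the reason for that patient's status. That comes from a cut-off on a point estimate with 30 patients and is not evidence about relatives. Likewise, removing 5 of 23 completers to give 18/30 = 60.0% would be pure assumption, and right only if all five were full proxies. Neither figure should carry the argument.

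**A tick-box is imperfect.** A relative could tick it wrongly, and help will be under-reported. This stands as a limit of the fix.

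**Conclusion.** The point holds in a limited form. The supplied summary names the patient as respondent but lists nothing that identifies who entered each form, so entry by a relative would go undetected, would count toward the 75% criterion, and could blur completion by autonomy, frailty and computer experience.

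The size depends on an unknown frequency. At an apparent 80% rate and an assumed 5% to 20% of completers depending on a relative, the patient-entered rate lies between 76% and 64%, and the chance of reaching the pass mark between 0.57 and 0.10 rather than 0.76. These figures assume 30 evaluable patients, independence between patients, and full proxy entry that decides completer status.

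A reader might go further and conclude that the feasibility verdict will be wrong, or that the subgroup contrasts are flattened. The documents give no rate of proxy entry and no evidence on who is helped, so they support neither conclusion. This is a cheap improvement to a descriptive pilot, not a fault in the calculation of the primary endpoint.

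**What to change.** 1. Add one closed item to each online form: *Filled in by: patient alone / patient with help / another person*. Keep it outside the items that define a complete form, so that the primary endpoint does not change.
2. Leave the primary rule, the 75% criterion and the sample size unchanged.
3. Prespecify a sensitivity analysis: the primary proportion counting only patient-entered forms (alone or with help), also split by alone versus with help. Use the same 95% confidence interval method as for the primary proportion.
4. Give the same breakdown in the tables of completion by patient characteristics.
5. Describe scores from forms entered by another person separately.

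The cost is one extra tap per form, one field in the tool and a few added lines in the analysis. Some help will still go unreported, so the patient-entered proportion should be presented as an approximate figure that may be too high.
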